8.9.9. Time Period and Frequency for Collecting AE and SAE Information

Medical occurrences that begin before the start of study intervention administration but after obtaining informed consent will be recorded in the Medical History/Current Medical Conditions section of the eCRF and not in the AE section; however, if the condition worsens at any time after study intervention administration, it will be recorded and reported as an AE.

Adverse events may be collected as follows:

- Observing the participant.
- Receiving an unsolicited complaint from the participant.
- Questioning the participant in an unbiased and nonleading manner.

All SAEs will be recorded and reported to the Sponsor or designee immediately and under no circumstance should this exceed 24 hours of becoming aware of the event, as indicated in [Section 8.10.2](#). The Investigator will submit any updated SAE data to the Sponsor within 24 hours of it being available.

Investigators are not obligated to actively seek AEs or SAEs after conclusion of the study participation (EoS). However, if an Investigator learns of any SAE, including a death, at any time after a participant has been discharged from the study and considers the event to be reasonably related to the study intervention or study participation, the Investigator must promptly notify the Sponsor.

8.9.10. Method of Detecting AEs and SAEs

eDiary has specifically been designed for this study by the Sponsor to collect solicited ARs. Refer to [Section 8.9.4](#) for further details on the use of eDiary. Details on recording of solicited ARs in an eDiary are included in [Section 8.10.3](#).

The Investigator is responsible for the documentation of AEs regardless of vaccination group or suspected causal relationship to the study intervention. For all AEs, the Investigator must pursue and obtain information adequate to determine the outcome of the AE and to assess whether the AE meets the criteria for classification as an SAE or AESI requiring immediate notification to the Sponsor or its designated representative.

Care will be taken not to introduce bias when detecting AEs and/or SAEs. Open ended and nonleading verbal questioning of the participant is the preferred method to inquire about AE occurrences.

8.9.11. Regulatory Reporting Requirements for SAEs

Prompt notification by the Investigator to the Sponsor of a SAE is essential so that legal obligations and ethical responsibilities towards the safety of participants and the safety of a study intervention under clinical investigation are met.

The Sponsor has a legal responsibility to notify both the local regulatory authority and other regulatory agencies about the safety of a study intervention under clinical investigation. The Sponsor will comply with country-specific regulatory requirements relating to safety reporting to the regulatory authority, IRB/IEC, and Investigators.

Safety reports must be prepared for suspected unexpected serious adverse reactions and will be forwarded to Investigators according to local regulatory requirements and Sponsor policy.

An Investigator who receives a safety report describing an SAE or other specific safety information (eg, summary or listing of SAEs) from the Sponsor will review and then file it along with the IB and will notify the IRB/IEC, if appropriate according to local requirements.

8.9.12. Blood Sampling Volumes

The maximum amount of blood collected from each participant over the duration of the study, including any extra assessments that may be required, will not exceed blood limits specified in the ICF. Repeat or unscheduled samples may be taken for safety reasons or for technical issues with the samples. Further details are provided in both the ICF and Laboratory Reference Manual.

8.9.13. Ancillary Supplies for Participant Use

Clinics will distribute Sponsor-provided oral thermometers and rulers for use by participants in assessing body temperature and injection site reactions for recording solicited ARs in the eDiary.

8.10. Safety Definitions

8.10.1. Adverse Event

An AE is defined as any untoward medical occurrence associated with the use of a drug in humans, whether or not considered drug related.

A treatment-emergent AE (TEAE) is defined as any event not present before exposure to the study intervention or any event already present that worsens in intensity or frequency after exposure.

Events Meeting the Adverse Event Definition

- Exacerbation of a chronic or intermittent pre-existing condition including either an increase in frequency and/or intensity of the condition.
- New conditions detected or diagnosed after the first dose of study intervention even though they may have been present before the start of the study.

Events NOT Meeting the Adverse Event Definition

- Procedures planned before study entry (eg, hospitalization for preplanned surgical procedure).
- Medical or surgical procedure (eg, endoscopy, appendectomy) - the condition that leads to the procedure should be the AE.
- Situations in which an untoward medical occurrence did not occur (social and/or convenience admission to a hospital).

An unsolicited AE is any AE reported by the participant that is not specified as a solicited AR (Section 8.10.3) in the protocol; or is specified as a solicited AR in the protocol, but starts outside the protocol-defined period for reporting solicited ARs (ie, for the 7 days after each dose of the study intervention).

8.10.2. Serious Adverse Events

An AE (including a solicited AR) is considered a SAE if it results in any of the following outcomes:

- **Results in Death**
- **Is life-threatening**
An AE is considered life-threatening if, in the view of either the Investigator or the Sponsor, its occurrence places the participant at immediate risk of death. It does not include an AE that, had it occurred in a more severe form, might have caused death.
- **Inpatient hospitalization or prolongation of existing hospitalization**
In general, inpatient hospitalization indicates the participant was admitted to the hospital or emergency ward for at least 1 overnight stay as an inpatient for observation and/or treatment that would not have been appropriate in the physician's office or outpatient setting. Complications that occur during inpatient hospitalization will be recorded as an AE; however, if a complication/AE prolongs hospitalization or otherwise fulfills SAE criteria, the complication/AE will be recorded as a separate SAE.
- **Persistent or significant disability or incapacity or substantial disruption of the ability to conduct normal life functions**
This definition is not intended to include experiences of relatively minor medical significance such as uncomplicated headache, nausea/vomiting, diarrhea, influenza, and accidental trauma (eg, sprained ankle) which may interfere with or prevent everyday life functions but do not constitute a substantial disruption (see Section 11.6 for country-specific amendment affecting this paragraph).
- **Congenital anomaly or birth defect**
- **Medically important event**
An AE is medically important if, per the medical judgment of the Investigator or the Sponsor, it is determined that SAE reporting is appropriate in other situations, such as important medical events that may not be immediately life-threatening or result in death or hospitalization, but may jeopardize the participant or require medical or surgical intervention to prevent one of the other outcomes listed in the above definition.

8.10.3. Solicited Adverse Reactions

Solicited ARs are a subset of AEs consisting of selected signs and symptoms that participants are asked to record/report. In this study, the solicited ARs are reactogenicity events. The term “reactogenicity” refers to the occurrence of transient adverse effects associated with vaccine administration. An eDiary will prompt daily participant reporting of solicited ARs using a structured checklist (Section 8.9.4). Participants will record such occurrences in the eDiary on the day of administration of study intervention and on each of the 6 days after dosing.

Severity grading of reactogenicity events will be automatically assigned upon participant entry into the eDiary based on the grading scales presented in Table 5, which are modified from the Toxicity Grading Scale for Healthy Adult and Adolescent Volunteers Enrolled in Preventative Vaccine Clinical Trials (DHHS 2007). All solicited ARs (local and systemic) will be considered causally related to dosing.

If a participant reports a solicited AR with onset during the solicited period, but they did not record the event in the eDiary, then the event should be recorded by study staff on the Reactogenicity page of the eCRF.

If the event starts during the solicited period, but continues beyond 7 days after dosing, the participants should notify the site to provide an end date and close out the event on the Reactogenicity page of the eCRF.

If the participant reported an event that started after the solicited period (ie, after Day 7), it should be recorded as an AE on the AE page of the eCRF. Causality for these events will be determined per assessment by the Investigator.

Any solicited AR that meets any of the following criteria must be entered into the participant’s source document and must also be recorded by the study site staff in the solicited AR section of the participant’s eCRF:

- Solicited AR that results in a visit to a healthcare practitioner (HCP) (MAAE).
- Solicited AR leading to the participant withdrawing from the study or the participant being withdrawn from the study by the Investigator (AE leading to withdrawal).
- Solicited AR lasting beyond 7 days post injection.
- Solicited AR that otherwise meets the definition of an SAE.

Table 5: Solicited Adverse Reactions and Grades

Reaction	Grade 1	Grade 2	Grade 3	Grade 4 ¹
Injection site pain	No interference with activity	Some interference with activity	Prevents daily activity	Emergency room (ER) visit or hospitalization
Injection site erythema (redness)	25 - 50 mm/ 2.5 - 5 cm	51 - 100 mm/ 5.1 - 10 cm	> 100 mm/ > 10 cm	Necrosis or exfoliative dermatitis

Reaction	Grade 1	Grade 2	Grade 3	Grade 4¹
Injection site swelling/induration (hardness)	25 - 50 mm/ 2.5 - 5 cm	51 - 100 mm/ 5.1 - 10 cm	> 100 mm/ > 10 cm	Necrosis
Axillary (underarm) swelling or tenderness ipsilateral to the side of injection*	No interference with activity	Some interference with activity	Prevents daily activity	ER visit or hospitalization
Headache	No interference with activity	Some interference with activity	Prevents daily activity	ER visit or hospitalization
Fatigue	No interference with activity	Some interference with activity	Prevents daily activity	ER visit or hospitalization
Myalgia (muscle aches all over body)	No interference with activity	Some interference with activity	Prevents daily activity	ER visit or hospitalization
Arthralgia (joint aches in several joints)	No interference with activity	Some interference with activity	Prevents daily activity	ER visit or hospitalization
Nausea/vomiting	No interference with activity or 1-2 episodes/ 24 hours	Some interference with activity or > 2 episodes/ 24 hours	Prevents daily activity, requires outpatient IV hydration	ER visit or hospitalization for hypotensive shock
Chills	No interference with activity	Some interference with activity not requiring medical intervention	Prevents daily activity and requires medical intervention	ER visit or hospitalization
Fever (oral)	38.0 – 38.4°C 100.4 – 101.1°F	38.5 – 38.9°C 101.2 – 102.0°F	39.0 – 40.0°C 102.1 – 104.0°F	> 40.0°C > 104.0°F

Abbreviation: ER = Emergency room.

Note: Events listed above but starting > 7 days post study injection will be recorded on the AE page of the eCRF.

Causality for each event reported on the AE page will be determined per assessment by the Investigator.

¹ Grading of Grade 4 events will be determined per Investigator and assessment is recorded on the reactogenicity event page in the electronic case report form.

Source: Guidance for Industry – Toxicity Grading Scale for Healthy Adult and Adolescent Volunteers Enrolled in Preventive Vaccine Clinical Trials (DHHS 2007).

8.10.4. Medically Attended Adverse Events

An MAAE is an AE that leads to an unscheduled visit to an HCP. This would include visits to a study clinic for unscheduled assessments (eg, rash assessment, abnormal laboratory follow-up) and visits to HCPs external to the study clinic (eg, emergency room, urgent care, primary care physician). Investigators will review unsolicited AEs for the occurrence of any MAAEs. Unsolicited AEs will be captured on the AE page of the eCRF.

An unscheduled visit for assessment of protocol-defined ILI (symptoms assessment and NP swab) is not considered an MAAE unless additional medical evaluation, including examinations/testing not required per protocol, and/or treatment is provided during the visit, **OR** if the participant meets RT-PCR confirmed influenza infection (RT-PCR with positive result for influenza) ([Section 8.10.5](#)).

8.10.5. Influenza-like Illness Case Definitions

Protocol-defined ILI:

A protocol-defined ILI is defined as body temperature $\geq 37.5^{\circ}\text{C}$ [$\geq 99.5^{\circ}\text{F}$] accompanied by at least 1 respiratory illness symptom (sore throat, cough, sputum production, wheezing, or difficulty breathing).

CDC-defined ILI:

A CDC-defined ILI is defined as body temperature $\geq 37.8^{\circ}\text{C}$ ($\geq 100^{\circ}\text{F}$) accompanied by cough and/or sore throat.

RT-PCR-confirmed Influenza Infection:

An RT-PCR-confirmed influenza infection is defined as a positive influenza result on a respiratory sample by RT-PCR within 7 days of onset of protocol- or CDC-defined ILI performed at any setting during the study period.

Culture-confirmed Influenza Infection:

Culture-defined ILI is defined as a positive influenza result by viral culture following a positive influenza result by RT-PCR. Viral cultures will only be done on samples with a positive influenza result by RT-PCR.

Similarity to Strains Selected for the Seasonal Vaccine:

A laboratory-confirmed isolate is deemed similar to one of the vaccine components if determined by antigenic testing of the cultured virus using specific antisera and/or by genetic sequencing of the HA segments showing identity of key antigenic residues with vaccine strain-like strains.

Antigenic Matched to Strains Selected for the Seasonal Vaccine

Culture-confirmed viruses are deemed to be antigenically similar to vaccine strains by antigenic testing of the cultured virus using specific antisera.

8.10.6. Adverse Events of Special Interest

An AESI is an AE (serious or nonserious) of scientific and medical concern specific to the Sponsor's product or program, for which ongoing monitoring and immediate notification by the

Investigator to the Sponsor are required. Such events may require further investigation to characterize and understand them.

AESIs for this protocol are described in [Section 11.4](#).

All AESIs will be collected through the entire study period and must be reported to the Sponsor or designee immediately and in all circumstances within 24 hours of becoming aware of the event via the electronic data capture system. If a site received a report of a new AESI from a participant or receives updated information on a previously reported AESI at a time after the eCRF has been taken offline, then the site should report this information on the paper SAE/AESI Report Form provided to the study site via email or fax as provided on the form ([Section 8.9.8](#)).

8.10.6.1. Anaphylaxis

All suspected (ie, related to study intervention) cases of anaphylaxis should be recorded as MAAEs and AESIs and reported as an SAE, based on the criteria for a medically important event, unless the event meets other serious criteria. As an SAE, the event should be reported to the Sponsor or designee immediately and in all circumstances within 24 hours, per [Section 8.9.8](#). The Investigator will submit any updated anaphylaxis case data to the Sponsor within 24 hours of it being available. For reporting purposes, a participant who displays signs or symptoms consistent with anaphylaxis (as below) should be reported as a potential case of anaphylaxis. This is provided as general guidance for Investigators and is based on the Brighton Collaboration case definition ([Rüggeberg et al 2007](#)).

Anaphylaxis is an acute hypersensitive reaction with multi-organ system involvement that can present as, or rapidly progress to, a severe life-threatening reaction. It may occur following exposure to allergens from a variety of sources.

Anaphylaxis is a clinical syndrome characterized by the following:

- Sudden onset AND
- Rapid progression of signs and symptoms AND
- Involves 2 or more organ systems, as follows:
 - **Skin/mucosal:** urticaria (hives), generalized erythema, angioedema, generalized pruritus with skin rash, generalized prickle sensation, red and itchy eyes.
 - **Cardiovascular:** measured hypotension, clinical diagnosis of uncompensated shock, loss of consciousness or decreased level of consciousness, evidence of reduced peripheral circulation.
 - **Respiratory:** bilateral wheeze (bronchospasm), difficulty breathing, stridor, upper airway swelling (lip, tongue, throat, uvula, or larynx), respiratory distress, persistent dry cough, hoarse voice, sensation of throat closure, sneezing, rhinorrhea.
 - **Gastrointestinal:** diarrhea, abdominal pain, nausea, vomiting.

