3. OBJECTIVES AND ENDPOINTS

The objectives which will be evaluated in this study and endpoints associated with each objective are provided in [Table 2](#).

Table 2: Study Objectives and Endpoints

Primary Objectives	Primary Endpoints

 To evaluate the safety and reactogenicity of mRNA-1010 during the treatment period (28 days after study intervention) and follow-up period (period following the treatment period). 	
 Solicited local and systemic ARs through 7 days after study injection. Unsolicited AEs through 28 days after study injection. MAAEs from Day 1 to Day 361 (Month 12)/EoS. AESIs from Day 1 to Day 361 (Month 12)/EoS. SAEs from Day 1 to Day 361 (Month 12)/EoS. AEs leading to discontinuation from Day 1 to Day 361 (Month 12)/EoS.

 To evaluate relative vaccine efficacy of mRNA-1010 as compared to an active comparator against influenza caused by any influenza A or B virus strains using protocol-defined ILI definition. 	
 First episode of RT-PCR confirmed protocol-defined ILI that begins at least 14 days post vaccination through Day 181 (Month 6)/end of influenza season caused by any seasonal influenza A or B virus strains regardless of antigenic match to strains selected for the seasonal vaccine.
Secondary Objectives	Secondary Endpoints

 To evaluate relative vaccine efficacy of mRNA-1010 vaccine as compared to an active comparator against influenza caused by influenza A or B strains with similarity^a to the vaccine strains, using protocol-defined ILI definition. 	
 First episode of RT-PCR-confirmed protocol defined ILI that begins at least 14 days post vaccination through Day 181 (Month 6)/end of influenza season caused by influenza A or B strains with similarity^a to those selected for the seasonal vaccine.

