11.4. APPENDIX 4: Adverse Events of Special Interest Terms

Investigators should report all events that fall into the categories presented in [Table 11](#) as an AESI per the reporting processes in [Section 8.9.8](#). These AESIs are medical concepts that are generally of interest in vaccine safety surveillance as per the Brighton Collaboration and Safety Platform for Emergency Vaccines.

Table 11: Adverse Events of Special Interest

Medical Concept	Additional Notes
Thrombocytopenia	
 • Platelet counts $< 150 \times 10^9$ • Including but not limited to immune thrombocytopenia, platelet production decreased, thrombocytopenia, thrombocytopenic purpura, thrombotic thrombocytopenic purpura, or HELLP syndrome
New onset of or worsening of the following neurologic diseases:	
 • Guillain-Barre Syndrome • Acute disseminated encephalomyelitis • Idiopathic peripheral facial nerve palsy (Bell’s palsy) • Seizures including but not limited to febrile seizures and/or generalized seizures/convulsions
Anaphylaxis	
 • Anaphylaxis as defined per protocol (Section 8.10.6.1) • Follow reporting procedures in Section 8.9.8
Myocarditis/Pericarditis	
 • Myocarditis • Pericarditis • Myopericarditis

Abbreviation: HELLP = hemolysis, elevated liver enzymes, and low platelet count.

11.5. APPENDIX 5: CDC Working Case Definitions of Pericarditis, Myocarditis, and Myopericarditis Occurring After Receipt of COVID-19 mRNA Vaccines

Table 12: Case Definitions of Probable and Confirmed Myocarditis, Pericarditis, and Myopericarditis

Condition	Definition	
Acute myocarditis	Probable case	Confirmed case
	Presence of ≥ 1 new or worsening of the following clinical symptoms: * 
 • Chest pain, pressure, or discomfort. • Dyspnea, shortness of breath, or pain with breathing. • Palpitations. • syncope. 	Presence of ≥ 1 new or worsening of the following clinical symptoms: * 
 • chest pain, pressure, or discomfort. • dyspnea, shortness of breath, or pain with breathing. • Palpitations. • Syncope.

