¹ Grading of Grade 4 events will be determined per Investigator and assessment is recorded on the reactogenicity event page in the electronic case report form.

Source: Guidance for Industry – Toxicity Grading Scale for Healthy Adult and Adolescent Volunteers Enrolled in Preventive Vaccine Clinical Trials ([DHHS2007](#)).

9.8. Appendix G Adverse Events of Special Interest Terms**Table 12: Adverse Events of Special Interest**

| Medical Concept | Additional Notes |
|---|--|
| Thrombocytopenia | 
 • Platelet counts < 150 × 10⁹ • Including but not limited to immune thrombocytopenia, platelet production decreased, thrombocytopenia, thrombocytopenic purpura, thrombotic thrombocytopenic purpura, or HELLP syndrome |
| New onset of or worsening of the following neurologic diseases: | 
 • Guillain-Barre Syndrome • Acute disseminated encephalomyelitis • Idiopathic peripheral facial nerve palsy (Bell's palsy) • Seizures including but not limited to febrile seizures and/or generalized seizures/convulsions |
| Anaphylaxis | 
 • Anaphylaxis as defined per protocol (Section Error! Reference source not found.) • Follow reporting procedures in the protocol (Section Error! Reference source not found.) |
| Myocarditis/Pericarditis | 
 • Myocarditis • Pericarditis • Myopericarditis |

Abbreviation: HELLP = hemolysis, elevated liver enzymes, and low platelet count.

9.9. Appendix H Severity Grading of Vital Sign Abnormalities**Table 13: Severity Grading of Vital Sign Abnormalities**

| Vital Signs* | Mild (Grade 1) | Moderate (Grade 2) | Severe (Grade 3) | Potentially Life Threatening (Grade 4) |
|---------------------------------------|------------------------------|------------------------------|--------------------------|--|
| Fever (°C)** (°F)** | 38.0 – 38.4 100.4 – 101.1 | 38.5 – 38.9 101.2 – 102.0 | 39.0 – 40 102.1 – 104 | > 40 > 104 |
| Tachycardia - beats per minute | 101 – 115 | 116 – 130 | > 130 | ER visit or hospitalization for arrhythmia |
| Bradycardia - beats per minute*** | 50 – 54 | 45 – 49 | < 45 | ER visit or hospitalization for arrhythmia |
| Hypertension (systolic) - mm Hg | 141 – 150 | 151 – 155 | > 155 | ER visit or hospitalization for malignant hypertension |
| Hypertension (diastolic) - mm Hg | 91 – 95 | 96 – 100 | > 100 | ER visit or hospitalization for malignant hypertension |

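### Protocol 8.10.6.1 ties AESI recording of anaphylaxis to relatedness while 8.10.6 and Appendix 4 do not, so the AESI flag may depend on causality opinion

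*Protocol*

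**What the plan says.** Protocol Table 2 (Section 3) lists "AESIs from Day 1 to Day 361 (Month 12)/EoS" among the primary safety endpoints, with no causality restriction. Section 8.10.6 describes an AESI as an adverse event, serious or not, that must be notified to the sponsor within 24 hours, and adds: "All AESIs will be collected through the entire study period". It sends the reader to Appendix 4 (Section 11.4) for the categories. Appendix 4 says "Investigators should report all events that fall into the categories presented in" its Table 11 as an AESI. The anaphylaxis row of that table reads "Anaphylaxis as defined per protocol (Section 8.10.6.1"), and SAP Appendix G, Table 12, likewise has "Anaphylaxis as defined per protocol".

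Section 8.10.6.1 begins: "All suspected (ie, related to study intervention) cases of anaphylaxis should be recorded as MAAEs and AESIs and reported as an SAE". Later in the same paragraph it says that, for reporting purposes, "a participant who displays signs or symptoms consistent with anaphylaxis (as below) should be reported as a potential case of anaphylaxis". Its clinical description covers sudden onset, rapid progression and involvement of at least two organ systems, and notes: "It may occur following exposure to allergens from a variety of sources".

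In SAP 6.7.2 the investigator decides whether an adverse event is also an AESI, and the planned AESI listing uses that assessment. The SAP also plans an anaphylactic-reaction summary by standardised MedDRA query (Tables 15 and 16), with no relatedness condition.

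**The concern.** Two instructions govern the same flag and they differ in scope. Appendix 4 is all-causality; the opening sentence of 8.10.6.1 covers cases judged related. Of the AESI categories, only anaphylaxis carries such wording. In the neighbouring rule for myocarditis and pericarditis (8.10.6.2), *suspected* expresses diagnostic certainty, so the same word has two meanings in adjacent rules.

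A safety comparison between randomised arms is most useful when an event is counted whatever the investigator thinks caused it, with causality reported alongside. If some sites flag every anaphylaxis and others only those they judge related, the AESI count mixes two definitions. An event judged unrelated could also miss the 24-hour AESI route.

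**Working it through.** The documents give no figure to reproduce, so the check sets the passages side by side and follows one case through them.

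**1. Does the cross-reference settle it?** Not fully. Appendix 4 and SAP Table 12 both point to the protocol definition. Section 8.10.6.1 holds two things: a clinical description with no relatedness element, and a recording rule with one. Read as a pointer to the description, the tables are all-causality. But a site that follows the pointer meets the recording rule first.

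**2. Does the later sentence in 8.10.6.1 remove the condition?** It supports the broad reading, because it covers anyone with consistent signs. It does not say that a potential case receives an AESI flag, and it is described as general guidance.

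**3. How narrow is the literal reading?** Section 8.10.8 classes an event as related only if the vaccine explains it better than another cause does. An episode with a plausible food or drug trigger would normally be classed as not related.

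**4. Follow one case:** an anaphylaxis after the 28-day window, judged not related.

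| Rule | Outcome |
|---|---|
| 8.10.6 with Appendix 4 | AESI, 24-hour report |
| 8.10.6.1, opening sentence read literally | No instruction to flag it as an AESI |
| 8.10.6.1, later sentence | Reported as a potential case; flag not named |
| 8.9.10 (documentation of AEs) | Applies whatever the suspected cause |
| 8.10.4 (MAAE) | Recorded if it led to an unscheduled visit to a practitioner |
| 8.10.2 and 8.9.8 (SAE) | Recorded, with a 24-hour report, if it meets a seriousness criterion |
| SAP SMQ summary | Found if recorded: the anaphylactic-reaction term alone qualifies (Category A) |

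Within the first 28 days the event would also be collected as an unsolicited AE (8.9.6). After that, a non-serious episode judged unrelated and without an unscheduled visit has the weakest route to capture, although 8.9.7 still asks for all observed or reported AEs. This gap is narrow.

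**5. Does the ambiguity reach the tables?** Yes, for the AESI summaries and listing, because the flag is the investigator's. The SMQ summary does not use the flag.

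**6. Scale.** Inputs are 11,500 participants per group (Protocol Table 3) and the two rates in Protocol 2.3.2.
- 11,500 × 2.5 / 1,000,000 = 0.029 expected cases per group.
- 11,500 / 450,000 = 0.026 expected cases per group.

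These are vaccine-associated rates. The first is for mRNA-1273 and the second for vaccines without allergens such as gelatin or egg protein; neither is shown to apply to both arms. They indicate only that related cases should be very rare. The number of unrelated cases, which is what the wording affects, needs a background rate that the documents do not give.

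**The case against.** The strongest reply is that there is no filter. Section 8.10.6.1 says what to do with related cases; it does not say that only related cases are AESIs. A site that flags every anaphylaxis complies with 8.10.6, 8.10.6.1 and Appendix 4 together, and the opening sentence can be read as an extra instruction giving related cases automatic MAAE and SAE status. The clinical description, with its mention of varied allergen sources, supports this. The reply is fair, and it limits the point to an ambiguity that could produce under-flagging. It does not remove the ambiguity, because a site following the bracket also has the protocol's words behind it.

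A reader might be tempted to go further in four ways that the documents do not support:
- **No all-causality comparison between arms is available.** The SMQ summary has no causality condition, and underlying AE, MAAE and SAE capture does not depend on relatedness.
- **The AESI and SMQ counts disagree because of the bracket.** They can differ anyway: one is investigator-assessed, while the other is a term algorithm that counts, for example, a single report of shock.
- **Nearly every anaphylaxis in the trial would be dropped.** That needs the missing background rate, and what could be lost is mainly the flag.
- **Unrelated cases escape expedited reporting.** Serious ones still go to the sponsor within 24 hours as SAEs; only non-serious ones could miss that route.

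**Conclusion.** The inconsistency is real and minor. Section 8.10.6.1 and Appendix 4 can be read to give different answers on whether an anaphylaxis judged unrelated is an AESI. The answer affects a component of a primary safety endpoint and, for non-serious cases, the 24-hour report. The likely consequence is a missing flag and uneven practice between sites. Loss of the event itself is unlikely, and no efficacy analysis is touched.

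This rests on two assumptions: that some sites would apply the opening sentence literally, and that events left unflagged are otherwise recorded so that the SMQ summary finds them. The SAP states no time window specific to that summary, so its coverage to Day 361 is also assumed. Investigators are blinded (Protocol 9.1), and the documents give no reason to expect under-flagging to favour one arm. The number of events affected cannot be computed; related cases alone would be about 0.03 per group at the protocol's quoted rates.

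**What to change.** Reconcile 8.10.6.1 with Section 11.4. State in 8.10.6.1 that every case meeting the listed clinical criteria is recorded as an AESI regardless of causality, with relatedness recorded as its own field under 8.10.8. Have the SAP say that the anaphylaxis AESI count is all-causality.

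Simply deleting the bracket would do more than this. One sentence governs AESI, MAAE and SAE recording together, so deletion would also make every unrelated anaphylaxis an automatic MAAE and SAE. The protocol should state separately whether that instruction is meant to cover unrelated cases.

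The cost is a small protocol wording change, a clarifying sentence in the SAP, a site memo and a few more 24-hour AESI reports, plus some additional SAE reports if the automatic instruction is widened as well.
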